4.4 Duration of the study

Patients will be treated with CYT107 or placebo for 4 weeks duration and undergo laboratory monitoring of various organ functions as detailed previously for the 28 days following the initial treatment. The ALC will be followed for an additional 14 days due to continuing effects of CYT107. Primary end points will be measured at approximately Day 42 +/- 3 days. Patient outcomes regarding secondary infections, readmission to hospitals, mortality, etc. will be followed at approximately 60, 90, 180 and 365 days after CYT107 therapy is initiated. Long term survival (1 year survival) will be recorded using a variety of means including physician records, patient telephone communication, and searches of mortality databases.

5. Study Population

5.1 Inclusion Criteria:

- 1) Patients of age ≥ 18 yrs to 80 yrs
- 2) Patients with persistent suspected sepsis at 48-120 hrs after admission
- 3) Two or more criteria for the systemic inflammatory response syndrome (SIRS) (see reference (19) for SIRS criteria) and a clinically or microbiologically suspected infection.
- 4) At least one organ failure as defined by a SOFA score of ≥ 2 at any time point during the 48-120 hrs after admission to the ICU
- 5) Requirement of vasopressor treatment as follows: i) epinephrine or norepinephrine at ≥ 0.05 $\mu\text{g}/\text{kg}/\text{min}$ ideal body weight; ii) vasopressin, or iii) dopamine at $\geq 4-5$ $\mu\text{g}/\text{kg}/\text{min}$ ideal body weight, continuously for 4 hrs or more, provided that at least 20 ml/kg of ideal body weight of crystalloid or an equivalent volume of colloid was administered during the 24-hour interval surrounding the start of vasopressor treatment, to maintain systolic pressure ≥ 90 mmHg or a mean arterial pressure ≥ 60 mmHg at any time point during their sepsis course preceding enrollment into the CYT107 study.
- 6) Lymphopenia with an absolute lymphocyte count ≤ 900 cells/ mm^3 at either the day of consent or the day prior to consent during their ICU stay
- 7) Predicted length of stay in the ICU of up to two weeks after starting drug therapy treatment in the trial
- 8) Ability to obtain a signed informed consent from patient or LAR consent.

5.2 Exclusion Criteria

- 1) Cancer with current chemotherapy or radiotherapy (Receipt of chemotherapy or radiotherapy within the last 6 weeks). All patients with current, or a history of, hematologic malignancy (including, but not limited to, ALL, AML, CLL, CML, etc.) or lymphoma will be excluded, regardless of receipt of recent chemotherapy.
- 2) Cardiopulmonary resuscitation within the previous 4 weeks without objective evidence of full neurologic recovery) or patients who have minimal chance of survival and are not expected to live > 3-5 days as defined by an APACHE II score of ≥ 35 at time of consideration for study eligibility.
- 3) Patients with a history of or who currently have evidence of autoimmune disease including for example: myasthenia gravis, Guillain Barre syndrome, systemic lupus erythematosus, multiple sclerosis, scleroderma, ulcerative colitis, Crohn's disease, autoimmune hepatitis, Wegener's etc.
- 4) Patients who have received solid organ transplant or bone marrow transplant
- 5) Patients with active or a history of acute or chronic lymphocytic leukemia
- 6) AIDS-defining illness (category C) diagnosed within the last 12 months prior to study entry
- 7) History of splenectomy
- 8) Any hematologic disease associated with hypersplenism, such as thalassemia, hereditary spherocytosis, Gaucher's Disease, and autoimmune hemolytic anemia
- 9) Pregnant or lactating women
- 10) Participation in another investigational interventional study within the last 6 months prior to study entry, with the exception of studies aimed at testing sedation products belonging to standard of care such as Propofol, Dexmedetomidine, Midazolam
- 11) Patients receiving immunosuppressive drugs, e.g., TNF-alpha inhibitors, for rheumatoid arthritis, inflammatory bowel disease or any other reason, or systemic corticosteroids other than hydrocortisone at a dose of ≤ 300 mg/day
- 12) Patients receiving concurrent immunotherapy or biologic agents; including growth factors, cytokines and interleukins other than the study medication, for example IL-2, growth factors, interferons, HIV vaccines, immunosuppressive drugs, hydroxyurea, immunoglobulins, adoptive cell therapy.

13) Prisoners

5.3 Study ID Numbers

Study ID numbers are assigned using an alpha-numeric sequence. The 2 first letters will signify the study center followed by sequential assignment of ID number in numerical order (WU-01, WU-02, etc. - Center ID numbers are defined in the center list- see Appendix). Each subject consented and enrolled will be assigned the next available number for the individual sites.

6. Study Visits and Procedures

All protocol related procedures are described in *Appendix II*: Flow charts of the study.

6.1 Screening period

The following procedures will be performed at the screening visit or during the screening period:

- Dated and signed patient informed consent (by the patient or family member)
- Each site will assign the subject the next available study ID number
- Inclusion/exclusion criteria checklist review
- Demographics, relevant medical/surgical history, Sepsis history, APACHE II score, SOFA score, GLASGOW coma scale
- Physical examination and lymphoid system examination
- 12-lead electrocardiogram (EKG) and interpretation (pretreatment EKG)
- Spleen ultrasound (Pre-treatment)
- Pregnancy test if female of childbearing potential without known contraceptive method
- Cardiac check: presence of vasopressors, EKG, MAP, HR, pHa
- Respiratory check: PaO₂, FiO₂ (A-a Grad if FiO₂ ≥ 0.5)
- Kidney functions: Creatinine, Urine analysis, 24hrs diuresis
- Liver function: ALT, AST, Bilirubin
- Sampling for:
 - Hematology (ALC, WBC, ANC, Mono, Platelets) and blood chemistry (including CRP, PT, PTT) as described in the flow chart,
 - PBMC for phenotyping and functionality test (CD3, CD4, CD8 T cells, HLA-DR expression, whole blood TNF-alpha production) as described in flow chart,

Data from laboratory tests and procedures performed as standard of care (SOC) during the screening period will be utilized for applying screening criteria. All remaining tests and procedures listed in Appendix 2 will be conducted for research purposes only and ordered by the PI.

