
Clinical and biological assessment
	
Medical History: A complete medical history of the patient will be obtained either by patient self-report, discussion with family if the patient is unable to provide a history, and review of the electronic medical records (EMR) of the patient.
 
Physical Examination: The physical exam findings will be obtained by examination of the electronic medical records (History & Physical).
 
Laboratory Studies: Results from standard of care laboratory tests as necessary to evaluate safety and efficacy of CYT107 will be obtained either by the EMR or Principal Investigator (PI) orders for research labs as detailed in Appendix 2- Flow Chart.
 
 • APACHE II and SOFA scores will be obtained by review of EMR and/or by the CYT107 Clinical Research Nurse Coordinator • Respiratory: oxygen saturation and inspired oxygen concentration • Imaging: ECG and spleen ultrasound • Hematology: hemoglobin, hematocrit, red blood cells, mean corpuscular volume, white blood count and differential, platelets, Prothrombin Time (PT) and partial thromboplastin time (PTT) • Chemistry: electrolytes (i.e., sodium, potassium, chloride, bicarbonate, calcium, and phosphorus), creatinine, glucose, albumin, liver function tests (total bilirubin, AST, ALT, Alkaline Phosphatase), and CRP (C-reactive protein). • Urinalysis: red blood cells • Pregnancy Tests in women of childbearing age without known contraceptive method (Serum or urine) • CYT107 Pharmacokinetics. Plasma levels of CYT107 will be assayed at various time points as specified (see Section 4.3.2 for details of timing of blood draws for PK studies. • Specific CYT107 binding and neutralizing antibody (at specialized labs only)
--	--

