6.2 Randomization

The randomization list will comprise three arms “CYT107 High frequency Arm” and “CYT107 Low frequency Arm”, and placebo Arm. A permuted-block randomization will be used in blocks of size of 3 and an allocation ratio of 1:1:1, stratified by study country (US and France). Subjects will be allocated randomly within each block. This procedure will be repeated until at

least 10 evaluable subjects are randomly assigned to each treatment group, totaling at least 30 evaluable subjects (between US and France).

Screening data, including lab results from screening and any relevant medical information, will be reviewed by the Research Nurse Coordinator and PI at each academic medical center for confirmation of all inclusion/exclusion criteria and randomization authorization.

After randomization authorization is granted by the PI at the responsible institution, the randomization assignment will be generated by computer. Each subject will be assigned the next available number. Subjects, investigators, and all study team members will be blinded to drug treatment. In the case of dropouts (either subject- or investigator-initiated), subjects will be replaced, to provide the required number of subjects. Randomization of replacements will be as follows:

1. Subjects withdrawn prior to randomization (prior to receiving CYT107 or placebo) will simply be replaced and the next subject will receive the same randomization assignment.
2. CYT107 treated subjects who are withdrawn after randomization while receiving the study drug treatments but prior to Day 14 will be replaced using with the next subject receiving the next randomization assignment. This will continue until a minimum of 10 patients have been randomized to each of the 3 cohorts and remained on study treatment through Day 13.
3. Subjects withdrawn or completing at least two weeks of study drug treatment will be considered evaluable and the following subject will receive the next scheduled randomization sequence.

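### Pregnancy excludes without exception, but the protocol text requires a pregnancy test only in women with no known contraceptive method, so an unrecognised pregnancy in the others could pass screening.

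*Protocol*

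**What the plan says.** The exclusion is unqualified. Item 9 of Protocol section 5.2 reads "Pregnant or lactating women", and the synopsis lists the same item. Neither makes an exception for contraceptive use.

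The test that would detect a pregnancy is qualified. Section 6.1 lists a "Pregnancy test if female of childbearing potential without known contraceptive method". The synopsis row on clinical and biological assessment says "Pregnancy Tests in women of childbearing age without known contraceptive method (Serum or urine" and so sets the same limit.

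Women of childbearing age can enter: section 5.1 sets "Patients of age ≥ 18 yrs to 80 yrs" with no restriction by sex.

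Two general provisions also bear on eligibility. Section 6.1 states: "Data from laboratory tests and procedures performed as standard of care (SOC) during the screening period will be utilized for applying screening criteria". Under section 6.2, screening data and relevant medical information "will be reviewed by the Research Nurse Coordinator and PI at each academic medical center for confirmation of all inclusion/exclusion criteria" before randomisation is authorised.

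The SAP says nothing on eligibility.

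**The concern.** The exclusion applies to all pregnant women, while the required test applies to only some of the women who could be pregnant. Recorded contraceptive use stands in for a negative test in the rest, yet a contraceptive method on record does not show that a woman is not pregnant.

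The record may also be weak in this setting. Patients are in intensive care, with organ failure and a vasopressor requirement, and consent may come from a representative. The synopsis allows the history to come from "discussion with family if the patient is unable to provide a history" and from the electronic record. A contraceptive entry obtained that way can be second-hand or out of date.

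What is at stake is mainly safety: fetal exposure to an investigational cytokine that, by the Protocol's own account, has not been tested in sepsis. There is also a small data consequence. Section 9.2.1.1 classes non-compliance with an exclusion criterion as a major deviation, and the target is only 10 evaluable patients per arm.

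**Working it through.** There is no stated figure to reproduce. The check sets the exclusion beside each step that could enforce it.

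1. **Who is excluded.** All pregnant women (synopsis; section 5.2, item 9).

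2. **Who must be tested.** Women of childbearing potential (section 6.1) or childbearing age (synopsis) for whom no contraceptive method is known. The limit appears in both places, so it is unlikely to be a slip in one of them.

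3. **Who is left out.** Women of childbearing potential with a contraceptive method on record. The term for a known method is not defined, and no verification is asked for. None of the eight inclusion criteria in section 5.1 concerns contraception, so no related criterion prompts a check.

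4. **Does another screening step cover them?** In part.
   - Routine-care results are used where they exist (section 6.1), but no routine-care pregnancy test is required.
   - History, physical examination and the eligibility checklist (section 6.1) would pick up a pregnancy that is known or evident.
   - The review by coordinator and investigator (section 6.2) works from the information gathered, which need not include a pregnancy test for these women.

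5. **Does a later step cover them?** Not in the text. The post-randomisation procedures (section 6.3) and the follow-up procedures (section 6.4) list no pregnancy test.

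6. **What remains.** A pregnancy is missed if three things hold together: a contraceptive method is on record, the pregnancy is neither known nor evident, and routine care has not tested for it. A site that carried out every listed screening step could then randomise a woman whom section 5.2 excludes.

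7. **Exposure if that happens.** Allocation is 1:1:1 with one placebo arm, so 2 of 3 assignments include CYT107. From the days listed in section 8.5:
   - High frequency: days 1, 4, 8, 11, 15, 18, 22, 25, which is 8 doses of CYT107.
   - Low frequency: days 1, 4, 8, 15, 22, which is 5 doses of CYT107, plus 3 of placebo.
   - Control: no CYT107.

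   These are maxima, because dosing ends at hospital discharge.

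8. **Data consequence.** One such patient would be 1/10 = 10% of an arm at the target of 10 evaluable patients. The SAP analyses everyone who received at least one dose, so she would stay in its analysis. Her place in the Protocol's per-protocol set would be settled at the data review meeting in section 9.2.1.1. No sample-size, power or error-rate figure changes.

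**The case against.** The strongest reply is that the Protocol does not rest on this one test. Routine-care results count, there is a history and an examination, and the coordinator and investigator must confirm every criterion before randomisation. A known or detected pregnancy excludes a woman whatever her contraceptive record. This stands. A reader might infer that these women are never tested, or that the exclusion cannot be enforced at all; the documents support neither. They support only that the text does not require a test in them.

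Second, section 6 points to the Appendix 2 flow chart for all procedures, and that chart was not in the text I worked from. It may ask for a test more widely. This also stands and limits certainty. If it does, the chart and the two text passages disagree and still need to be aligned.

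Third, the exemption needs a method that is known. If neither patient, family nor record establishes one, the test is required. The passage about family concerns medical history in general and does not mention contraception. This is fair: the gap needs a wrong or outdated record, or contraceptive failure, and nothing in the documents shows that either is common.

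Fourth, other exclusions, such as lactation and previous splenectomy, have no dedicated test, so a conditional test beside an unconditional exclusion is not a contradiction in the strict sense. I accept that it is not a strict contradiction. The comparison is weaker than it looks, though. History and examination usually settle those conditions, and a spleen ultrasound is done at screening. For pregnancy the Protocol itself chose a test as the means of checking, then withheld it from part of the group to which the exclusion applies.

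**Conclusion.** The concern holds in a limited form. As written, the required screening test does not cover every woman to whom the pregnancy exclusion applies. The uncovered case is a pregnancy that is not already known, evident or found by routine care, in a woman with a contraceptive method on record. If she is randomised to an active arm, she could receive up to 8 or up to 5 doses of CYT107, depending on the arm.

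A reader might want a probability of exposure. The documents give no number of women of childbearing potential, no rate of contraceptive use and no rate of unrecognised pregnancy, so any figure would consist of assumptions. It would also have to leave out the third of patients allocated to placebo. I give none, and the conclusion does not need one: it follows from comparing the exclusion with the testing rule. The event is likely to be rare in a trial of 30 evaluable patients, but it would be serious and is cheap to prevent.

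The conclusion assumes that the Appendix 2 flow chart does not already require a wider test. The effect is on patient safety and eligibility compliance, not on the statistical design.

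**What to change.** Reconcile the two testing passages (synopsis, clinical and biological assessment; section 6.1) with the exclusion (synopsis; section 5.2, item 9), so that the screening check covers every woman to whom the exclusion applies. Deleting the closing four words of "Pregnancy test if female of childbearing potential without known contraceptive method", and the same four words in the synopsis, does this. Make the same deletion in the Appendix 2 flow chart if it carries the limit. The edit is also a chance to use one term throughout, since the synopsis speaks of age and section 6.1 of potential.

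The cost is a wording change in two text passages, and possibly the flow chart, plus a few extra serum or urine hCG tests. Blood sampling and urine analysis are already part of screening, so no extra visit or staff is needed. Nothing in the sample size or the SAP has to change.

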6.2 Randomization

The randomization list will comprise three arms “CYT107 High frequency Arm” and “CYT107 Low frequency Arm”, and placebo Arm. A permuted-block randomization will be used in blocks of size of 3 and an allocation ratio of 1:1:1, stratified by study country (US and France). Subjects will be allocated randomly within each block. This procedure will be repeated until at

least 10 evaluable subjects are randomly assigned to each treatment group, totaling at least 30 evaluable subjects (between US and France).

Screening data, including lab results from screening and any relevant medical information, will be reviewed by the Research Nurse Coordinator and PI at each academic medical center for confirmation of all inclusion/exclusion criteria and randomization authorization.

After randomization authorization is granted by the PI at the responsible institution, the randomization assignment will be generated by computer. Each subject will be assigned the next available number. Subjects, investigators, and all study team members will be blinded to drug treatment. In the case of dropouts (either subject- or investigator-initiated), subjects will be replaced, to provide the required number of subjects. Randomization of replacements will be as follows:

1. Subjects withdrawn prior to randomization (prior to receiving CYT107 or placebo) will simply be replaced and the next subject will receive the same randomization assignment.
2. CYT107 treated subjects who are withdrawn after randomization while receiving the study drug treatments but prior to Day 14 will be replaced using with the next subject receiving the next randomization assignment. This will continue until a minimum of 10 patients have been randomized to each of the 3 cohorts and remained on study treatment through Day 13.
3. Subjects withdrawn or completing at least two weeks of study drug treatment will be considered evaluable and the following subject will receive the next scheduled randomization sequence.

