4.2 Study Treatment

Up to thirty patients may be enrolled at 4 sites in the US, i.e., Vanderbilt, Ohio State, University of Florida, and Washington University School of Medicine, however, it is anticipated that the initial enrollment of 30 subjects will occur at Vanderbilt, Washington University and Limoges in France. (Note: the French sites may also enroll up to 30 patients such that a total of 30 evaluable patients will be available from the two countries). In the event that patient accrual is delayed in one country, all patients will be recruited from either the US or France alone. A computerized protocol will implement permuted block randomization in blocks of size three. This scheme ensures balance across the treatment groups for every third randomization. A maximum of 20 septic patients will be treated with CYT107 at a dose of 10µg/kg. There will be two dosing regimens as illustrated in Figure 8 (below). CYT107 will be administered intramuscularly at the dose of 10µg/kg (IBW), once or twice a week for a four week cycle. Ten septic patients will have CYT107 administered twice a week for 4 weeks. Ten septic patients will have two doses of CYT107 administered during the first week followed by one dose of CYT107 in conjunction with 1 dose of placebo for 3 additional weeks. Ten septic patients will receive placebo twice a week for four weeks along with routine standard of care per the clinical providers.

At approx. 48-120 hrs **after admission** for sepsis, those septic patients who meet the Inclusion/Exclusion criteria (see previous section) and provided written informed consent, will be entered into the study. The first dose of CYT107 (as indicated below) is at approx. 48-120 hrs after sepsis onset. The initial dose of study drug will be administered only in the ICU by the PI or research nurse. If patients have an INR greater than 2.5 or a platelet count less than 35,000, CYT107 will be administered by the subcutaneous route rather than by intra-muscular injection.

A staggered approach to CYT107 treatment will be used in which treatment will not be initiated in a newly enrolled patient until 24 hours after the previously enrolled patient has received the second dose of CYT107 without evidence of serious adverse event (SAE) occurrence.

In patients with coagulopathy (INR greater than 2.5 or a platelet count less than 35,000), CYT107 will be administrated subcutaneously.

Figure 8 Schematic study design of CYT107 Protocol

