schematic "preliminary study" design																																																		
	Week 1							Week 2							Week 3							Week 4					Week 5				Week 6																			
days	1	2	3	4	5	6	7	8	9	10	11	12	13	14	15	16	17	18	19	20	21	22	23	24	25	...	28	29	...	35	36	...	42																	
IL-7	X			X				X			X				X			X				X			X																									
	X			X				X			P				X			P				X			P																									
PBO	P			P				P			P				P			P				P			P																									
ALC	X			X				X			X				X			X				X			X			X					X												X					
	TREATMENT																												FOLLOW UP																					
	IL-7 admin in 10 patients "high frequency dosing"																																																	
	IL-7 admin in 10 patients "low frequency dosing"																																																	
	10 Placebo Controls																					determination of ALC recovery and IL-7 clinical tolerance																												
	Absolute Lympho Counts																																																	

Dosing regimen for CYT107 in septic patients showed administration details of the “high frequency dosing” – (shown in red color) or the low frequency dosing (shown in blue color). The ALC is quantitated weekly throughout 6 weeks duration. Given that CYT107 will boost host immunity, we predict that patients treated with CYT107 will have decreased incidence of new secondary infection, decreased hospital readmissions (which generally are due to new secondary infections), and improved 60 day, 90 day, 180 days and one year mortality. Thus, these parameters will be recorded in all patients. The 60 day, 90 day, and one year data will be obtained by telephone interview, physician records, or by interrogating appropriate databases and newspaper obituary records. The patients will not have to be seen in clinic.

Additional experimental details:

- Patients with severe sepsis and organ failure who are admitted to the ICU are candidates. Septic patients who are not being treated in the ICU are not candidates for study enrollment.
- Septic patients will continue to receive the CYT107 to complete the full dose schedule even if their sepsis has resolved if they remain in the acute care hospital setting. Patients will not receive additional doses of CYT107 if they are discharged from the hospital.

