8.7.2 Unblinding

Emergency unblinding of the patient should only be undertaken by the investigator when it is essential to treat the subject safely and efficaciously. Most often, study drug discontinuation and knowledge of the possible treatment assignments are sufficient to treat a study subject who presents with an emergency condition. The investigator will make be responsible for making a decision to unblind in case of a suspected unexpected serious adverse reaction (SUSAR). The investigator will obtain the randomization assignment and a blinded alert will be sent to RevImmune, the coordinating center and the study team that a patient has been unblinded. The patient will be followed until resolution of the adverse event. All “end of study” assessments must be performed.

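### The protocol discloses a fixed block of 3 for three arms in a serial-entry trial with unmasked ALC, so the last allocation in each block is partly predictable; varying and undisclosed block sizes would reduce this cheaply.

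*Protocol*

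**What the plan says.** Block size is given twice in the protocol: "A permuted-block randomization will be used in blocks of size of 3" (6.2 Randomization) and "A computerized protocol will implement permuted block randomization in blocks of size three" (4.2 Study Treatment). Section 4.2 adds the consequence: "This scheme ensures balance across the treatment groups for every third randomization". Section 6.2 specifies "an allocation ratio of 1:1:1, stratified by study country (US and France"). Neither document mentions a varying or concealed size.

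Entry is serial: "treatment will not be initiated in a newly enrolled patient until 24 hours after the previously enrolled patient has received the second dose" (4.2). The same section expects the first 30 patients to come from two US sites and one French site, and allows all recruitment to come from one country.

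On what sites can see, section 4.2 says "The ALC is quantitated weekly throughout 6 weeks duration". The synopsis, under clinical and biological assessment, says "Results from standard of care laboratory tests as necessary to evaluate safety and efficacy of CYT107 will be obtained either by the EMR" or through orders by the principal investigator. Section 4.3.2, in a remark about the pooled analysis, says that all centres will see the results. No passage withholds post-baseline ALC from investigators, although none says outright that treating staff see it.

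Under 6.2 the site's principal investigator authorises each randomisation after confirming eligibility. Eligibility includes a predicted length of ICU stay (5.1).

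**The concern.** When the block size equals the number of arms and is known to the sites, each block of three contains each arm exactly once. Anyone who knows or suspects the first two arms knows or suspects the third before deciding whether to enter the next patient. Blinding is the only barrier, and the primary outcome is itself a laboratory value that may be read at the bedside. The protocol expects it to behave very differently on drug and on placebo.

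The stake is selection at entry. An investigator who expects a given arm next could, even unconsciously, judge a borderline criterion differently. With 10 evaluable patients per arm, a few steered entries could matter. Sample size and power are not in question.

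**Working it through.** **Inputs.** Fixed block of 3, arms High (H), Low (L) and Placebo (P), 1:1:1 (4.2, 6.2). Anticipated proportion with an ALC rise of over 50% by day 42: above 80% on either CYT107 regimen and below 20% on placebo (9.1); I use 0.80, 0.80 and 0.20. The documents give no figure for predictability. The one related figure, power above 85% at these rates with 10 per arm, reproduces: exact enumeration of the three-arm likelihood ratio test at 0.05 gives 86.0%.

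**1. Upper bound: all earlier arms known exactly.**
- Best-guess rate by position in the block: 1/3, 1/2, 1. Mean = (1/3 + 1/2 + 1)/3 = 0.611.
- Certain allocations: the third in each block, 1/3 = 33.3%, or 10 of 30.
- If only active versus placebo is known, position 3 is always certain, and position 2 is certain when the first patient had placebo: (0 + 1/3 + 1)/3 = 44.4%, about 13 of 30.

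**2. ALC response as the only clue, third patient in the block.** Placebo sits in position 1, 2 or 3 with probability 1/3 each. The likelihoods of the first two results are, in that order:

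| First two patients | P in position 1 | P in position 2 | P in position 3 | Probability of this result | Chance third is placebo |
|---|---|---|---|---|---|
| both respond | 0.2×0.8 = 0.16 | 0.8×0.2 = 0.16 | 0.8×0.8 = 0.64 | 0.96/3 = 0.32 | 0.64/0.96 = 0.667 |
| exactly one responds (two orders) | 0.04 or 0.64 | 0.64 or 0.04 | 0.16 | 2×0.84/3 = 0.56 | 0.16/0.84 = 0.190 |
| neither responds | 0.8×0.2 = 0.16 | 0.2×0.8 = 0.16 | 0.2×0.2 = 0.04 | 0.36/3 = 0.12 | 0.04/0.36 = 0.111 |

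- Active versus placebo, best guess: 0.32×0.667 + 0.56×0.810 + 0.12×0.889 = 0.773. Always guessing active gives 0.667.
- Exact arm, best guess: 0.32×0.667 + 0.56×0.405 + 0.12×0.444 = 0.493, against 0.333 by chance. H and L share the active probability equally because ALC does not separate them.
- Averaged over the three positions, the exact-arm rate is (33.3 + 43.3 + 49.3)/3 = 42.0%. The active-versus-placebo rate is (66.7 + 66.7 + 77.3)/3 = 70.2%, which is 3.6 points above always guessing active.
- No allocation is certain.

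If ALC separated the arms more sharply than the protocol assumes, accuracy for the third patient as active or placebo would be 87.7% at assumed rates of 90%/10% and 93.6% at 95%/5%.

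**3. Timing.** The second dose is on day 4, so the next patient can start on the previous patient's day 5. At the fastest pace the third patient starts when the first is at about day 9 and the second at about day 5. The response rates in step 2 refer to day 42, so step 2 is itself generous at fast accrual and nearer the mark at slow accrual.

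**4. Randomly mixed blocks of 3 and 6.** Assume equal chance of either size, sizes unknown to sites, and all earlier arms known. Simulating 20,000 lists of 30 gives 8.3% of allocations certain and a best-guess rate of 57.3%, against 33.3% and 61.1% for fixed blocks of 3.

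**5. Balance.** A block of 3 left incomplete leaves a gap of at most 1 between arms, so at most 2 over two countries. A block of 6 left incomplete can leave a gap of 2, so up to 4 over two countries. These are counts of randomised patients.

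**The case against.** The protocol has real safeguards. Allocation is central and computerised (4.1), and the assignment is generated only after authorisation (6.2). Placebo has the same volume and schedule as drug (8.4, synopsis), and only the pharmacist is unblinded (8.7.1). The list runs by country while study numbers run by site (5.3), so a patient's number does not show the position in the block. A block of 3 also keeps a very small trial closely balanced while non-evaluable patients are replaced. All of this stands. It makes prediction harder, but it does not remove the constraint that a disclosed block of 3 imposes. With one expected French site, one site may hold the whole French list, and the stagger rule itself requires someone to follow entry order.

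A reader might go further and infer that ALC reveals every third allocation. The documents do not support that. High and Low have the same anticipated response and identical dosing until day 11 (8.5), and response at 80% versus 20% yields a probability, not proof. Nor does the protocol expect ALC to double: the doubling in 9.1 is of CD4 T cells in HIV patients, and the expectation for ALC in sepsis is a rise of over 50% by day 42.

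Emergency unblinding, where "The investigator will obtain the randomization assignment" (8.7.2), adds little. It is reserved for essential need, and one disclosure fixes no other exact arm, although a disclosed placebo would show the other two in its block to be active.

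**Conclusion.** The predictability is real and avoidable, but modest on the protocol's own assumptions. The 33% certain and 61% best-guess figures are an upper bound that requires exact knowledge of every earlier arm. With ALC as the only clue, the third patient in a block is guessed correctly 49% of the time by exact arm and 77% as active or placebo, and two responders raise the chance that the third is placebo from 33% to 67%. These figures assume that the eventual response of both earlier patients is known at the time of entry, that ALC is open to the person judging eligibility, and that this person knows the patient's position in the country's list. At the fastest accrual the first assumption largely fails. Nothing in the documents shows that selection will occur, and no figure in the plan is wrong. This is a cheap improvement, not a flaw that threatens the trial.

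**What to change.** Generate the list with blocks of 3 and 6 in random order within country. Delete the block size from sections 4.2 and 6.2, together with the sentence in 4.2 on balance at every third randomisation; state only that permuted blocks stratified by country are used. Keep the sizes in a randomisation document restricted to the randomisation centre and unblinded staff who need it.

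The cost is a new list from the same system and a short amendment; the sample size and analysis do not change. The main gain is in certainty, since the best-guess rate falls by only about 4 points. The downside is looser balance, with the larger possible gap shown above. Because enrolment continues until each arm has 10 evaluable patients, this could mean a few extra patients.
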